## **1. EXECUTIVE SUMMARY**

#### 1.1 The RISE Consortium

The RISE Consortium is a collaborative effort involving investigators at 7 clinical centers who will determine the feasibility of different interventions in adults and children to preserve ß-cell function in individuals with prediabetes or mild, recently diagnosed type 2 diabetes. The Consortium involves three protocols:

- Three adult centers will perform a randomized, blinded, placebo-controlled trial comparing metformin, insulin glargine followed by metformin, or metformin plus liraglutide.
- Four pediatric centers will perform a randomized trial comparing metformin with metformin plus liraglutide.
- One adult center will perform a randomized trial comparing metformin with gastric band surgery.

To the greatest degree possible, the three protocols will use the same inclusion and exclusion criteria, study procedures, time line and outcome measures to allow for comparisons between groups and interventions. The protocol for the single adult center comparing metformin to gastric banding is presented here and is called the BetaFat Study

#### **1.2 Specific Aims and Objectives**

Type 2 diabetes (T2D) develops from progressive loss of pancreatic  $\beta$ -cell compensation for chronic insulin resistance. The loss of compensation occurs for years prior to the development of diabetes and continues after the diagnosis is made. Loss of compensation is caused by loss of β-cell mass and reduced function of individual β-cells. Several lines of evidence suggest that obesity and its adverse metabolic effects are primary drivers of falling βcell compensation. First, obesity is a well-known risk factor for T2D. Second, weight gain is an important predictor of falling  $\beta$ -cell compensation, an effect explained in our prior studies by insulin resistance and separate effects of low-grade inflammation and falling adiponectin levels. Third, treatment of obesity with lifestyle modification reduces the risk of diabetes in a pattern that suggests slowing, but not arrest of the  $\beta$ -cell disease. Protection is limited by weight regain, even in the relatively controlled setting of clinical trials. Fourth, treatment with thiazolidindiones, which mitigate some of the metabolic effects of obesity, can slow or even stop the loss of  $\beta$ -cell compensation. The protective effect is closely related to "unloading" of  $\beta$ cells through amelioration of insulin resistance; it occurs only in a subset of treated individuals. These four findings point to mitigation of excess adiposity as an important approach to arrest or reverse the  $\beta$ -cell disease that causes T2D. The findings also highlight important limitations in current behavioral and pharmacological approaches to  $\beta$ -cell preservation.

The present proposal seeks to expand clinical and scientific knowledge about  $\beta$ -cell preservation or restoration through mitigation of the metabolic effects of obesity. Specifically, we propose to compare weight loss induced by gastric banding to the standard pharmacological approach, metformin, for effects on  $\beta$ -cell function in pre- and mild T2D. Banding will reduce

adverse effects of obesity through weight loss that is more than can be sustained with lifestyle modification and which occurs without the potential confounding effect of direct stimulation of insulin secretion seen with operations that bypass the foregut. Metformin treatment will reduce insulin resistance and lower glucose levels. By comparing changes in  $\beta$ -cell function between treatment groups, we will compare the most commonly used medical monotherapy to a surgical approach for long-term effects on  $\beta$ -cell health. By examining changes in potential mediators of fat-induced  $\beta$ -cell deterioration, we may identify mechanisms for  $\beta$ -cell preservation that could serve as future therapeutic targets or markers of response to treatment. Based on data from weight loss and metformin in extant diabetes prevention trials and the greater weight loss expected with banding, we hypothesize that gastric banding will be more effective than metformin treatment at preserving or restoring  $\beta$ -cell function. We propose three specific aims to test this hypothesis and examine potential mechanisms for  $\beta$ -cell preservation or restoration.

**AIM 1 – Clinical Study:** We will conduct a prospective, randomized, 24-month study in obese individuals with pre-diabetes or mild T2D using two different approaches to mitigate the metabolic effects of obesity: (a) gastric banding and (b) metformin.

AIM 2 – Impact on  $\beta$ -cell Health: We will compare changes in markers of  $\beta$ -cell health, primarily  $\beta$ -cell compensation for insulin resistance, between groups. We predict that banding will improve  $\beta$ -cell health more than metformin will.

AIM 3 – Mechanisms Linking Fat to  $\beta$ -cell Health: We will measure body fat (total and regional by DEXA, abdominal distribution by MRI), along with potential circulating mediators of  $\beta$ -cell decline and use regression methods to identify mechanisms by which obesity may influence  $\beta$ -cell health and identify clinical markers thereof.

## **1.3 Overall Design and Study Interventions**

BetaFat is a two arm, unblinded study in which volunteers with prediabetes or drug-naïve, recent onset, mild type 2 diabetes will be randomized to: (1) metformin or (2) gastric banding. The study will recruit patients over a 27-month period and follow each individual for a total of 24 months on study intervention. The primary outcomes will be  $\beta$ -cell compensation for insulin resistance, measured in two ways as defined below. The anticipated duration of the BetaFat study is five years, including pre-trial preparation and post-trial analysis and reporting.

ß-cell function,  $\alpha$ -cell function, insulin sensitivity and glucose tolerance will be assessed using intravenous and oral tests. Both intravenous and oral tests will be obtained at baseline and after 12 and 24 months of therapy. Use of oral and intravenous tests will allow us to examine different aspects of  $\beta$ -cell function. Such use will also allow us to examine how well relatively simple measures of  $\beta$ -cell function,  $\alpha$ -cell function and insulin sensitivity (i.e., from fasting samples and oral glucose tolerance tests) correlate to more sophisticated measures (i.e., from glucose clamp studies) in the prediction of  $\beta$ -cell decline and/or response to treatment. Finally, a series of adipokines/inflammatory markers will be measured to determine whether they predict changes in  $\beta$ - and  $\alpha$ -cell function, insulin sensitivity and glucose tolerance without and with therapy.

Clinically, the project will serve as a test of concept for use of gastric banding relatively early in the spectrum of obesity and  $\beta$ -cell disease. We will derive information on the extent of weight loss necessary to fully arrest or reverse the  $\beta$ -cell disease, as well as potential clinical markers for successful treatment. Biologically, the results will provide crucial information on potential mediators of  $\beta$ -cell failure and its arrest or reversal in the context of obesity. Those mediators will guide the development of more effective strategies for prevention and early treatment of T2D with the aim of arresting or reversing the progressive  $\beta$ -cell disease.

# 2 BACKGROUND and SIGNIFIGANCE

## 2.1. Type 2 Diabetes: The Problem and its Importance

Type 2 diabetes is epidemic in developed and developing countries, where the disease affects approximately 5-10% of adults. Approximately twice as many people have impaired glucose levels and are at high risk for T2D. Prevalence and incidence rates of T2D and impaired glucose levels are on the rise, shadowing increasing rates of obesity. Projections place the number of people with diabetes in excess of 400 million by 2030 if nothing is done to stem these rising tides. Morbidity and mortality from acute and, especially chronic complications of T2D will follow. *Thus, development of effective strategies to prevent T2D and/or treat it once it develops is an extremely important public health issue across the globe*.

## 2.2 Disease Modification: Focus on Detrimental Effects of Obesity

The biology of T2D is characterized by progressive loss of pancreatic  $\beta$ -cell compensation for chronic insulin resistance (1-3). The progressive  $\beta$ -cell disease is present for years during the development of diabetes and it continues for many years after the diagnosis is made. The clinical face of this progressive disease is hyperglycemia that becomes harder and harder to treat. Many patients end up with severe insulin deficiency which, with their insulin resistance, makes it difficult or impossible to maintain low risk glucose levels. *Arrest or reversal of this progressive*  $\beta$ -cell disease is fundamental to effective prevention and treatment of T2D.

Toxicity from glucose and fatty acids (4), protein malfolding (5-7), and oxidative stress (8) are some processes that have been implicated in the loss of  $\beta$ -cell mass and function. In our own longitudinal studies of Hispanic women at high risk for T2D, declining  $\beta$ -cell compensation was most closely associated with weight gain (9). The association was explained statistically by covariate adjustment for three independent factors: increasing insulin resistance, rising levels of C-reactive protein and falling levels of adiponectin. *These findings suggest that obesity drives progressive*  $\beta$ -cell decompensation both indirectly (through insulin resistance and  $\beta$ -cell loading) and directly (through circulating adipocytokines acting on  $\beta$ -cells).

Based on these observations, we believe that mitigating the detrimental effects of obesity on  $\beta$ -cells is the most attractive strategy for arresting or reversing the progressive  $\beta$ -cell disease that causes and worsens T2D.

Theoretically, mitigation could be accomplished by reducing body fat or by ameliorating its adverse effects on  $\beta$ -cells. Clinical studies of prevention and early treatment of T2D support both approaches. Lifestyle modifications in the Finnish Diabetes Prevention Study (DPS) (10)

and the U.S. Diabetes Prevention Program (DPP) (11) achieved relatively modest weight loss that was partially sustained during 4-6 years of follow-up. The result was a 58% reduction in the diabetes incidence rate in each study. Protection from diabetes was more closely associated with weight loss than with increased physical activity (11). On average, the onset of diabetes was delayed ~2 years during the active treatment phase of the DPP (Fig 2 of REF (11)). It is not clear how many subjects actually stopped progressing toward diabetes, but clearly many did not. *Thus, modest weight loss may slow, but not arrest deterioration to T2D*.

We used thiazolidinediones to modify fat biology in the absence of weight loss. Subjects were Hispanic women with recent gestational diabetes. We observed a 55% reduction in diabetes rates over ~3.5 years (TRIPOD) (12). Importantly,  $\beta$ -cell compensation was fully stabilized in ~1/3 of the treated women. Protection from diabetes was very closely associated with  $\beta$ -cell "unloading", the term we have used to describe reductions in insulin secretory demands that occurred in response to insulin sensitization. The relationship between unloading and protection from diabetes was confirmed in a second study (PIOOD) (13). At least two other studies have demonstrated diabetes risk reductions of 62-72% with TZDs (14;15).

These studies demonstrate **three concepts that are fundamental to the present proposal.** First, reducing body fat or reducing its adverse metabolic effects in moderately obese individuals (average BMI was 30-35 in all studies) can slow rates of deterioration toward T2D. Second, the  $\beta$ -cell disease that causes T2D can be stopped through sufficient  $\beta$ -cell "unloading" or, possibly, related mechanisms. Third, neither modest weight loss nor TZD treatment is fully and uniformly effective in arresting progression toward and to T2D. There is great need to develop more potent approaches to  $\beta$ -cell preservation or restoration in pre- and mild T2D. The present proposal is designed as a test of concept for one such approach – weight loss induced by gastric banding – using metformin treatment as a comparator.

## 2.3 Rationale for Interventions

We considered a number of approaches. We rejected approaches based on stimulation of insulin secretion because our own data (12;13) and data from ADOPT (16) support the opposite approach. GLP-1 based therapies could have direct effects to enhance  $\beta$ -cell mass based on rodent studies (17), but available human data don't support such an effect in humans (18). The limits of lifestyle interventions are apparent from the DPP and DPS (10;11). Thiazolidinediones (TZDs) have a strong effect to preserve  $\beta$ -cell function in pre-diabetes (12;13), but the one available TZD, pioglitazone, has recently been linked to an increase in bladder cancer (19). Finally, basal insulin treatment could reduce insulin secretory demands, but had only a small effect on diabetes risk reduction in the ORIGIN trial (20). Thus, we concluded that we could either take an approach that would combine two or more of these approaches in a mechanistically logical fashion, or we could take a bolder approach directed at what we believe to be a primary drive of  $\beta$ -cell decline – adverse metabolic effects of obesity. We chose the latter option and believe we can make important contributions to studies that will operate under the RISE Consortium.

We chose gastric banding as the primary experimental treatment because (a) it induces 2-3 times the weight loss that can be achieved and sustained with even aggressive lifestyle

programs like the DPP ((21) and Figure 2.1); (b) It can reverse T2D (21); (c) it is not associated with the large stimulation of insulin secretion that appears to occur with foregut exclusion operations (22); (d) it is relatively non-invasive and safe compared to other bariatric procedures; and (e) the LapBand has recently been approved by the FDA for clinical use down to a BMI of 30 kg/m^2. The trend toward lower BMI thresholds for gastric banding provides both an opportunity and a need to study carefully the metabolic impact of the procedure in the presence of moderate obesity. We will apply banding to people with moderate obesity to maximize improvement in insulin sensitivity for any degree of weight loss (Figure 2.2).

#### Figure 2.1: Weight Loss in USC Gastric Band Program

Data are from 83 obese individuals with T2D who had follow-up for at least two years. Results were achieved without the intensive approach to band adjustment that we propose for this project.

Data are from 1221 adults (mean age 35 years, mean BMI 29.6 kg/m^2). Insulin sensitivity ( $S_1$ ) was measured with IVGTT-minimal model.

We chose metformin as the comparator for two main reasons. First, we will include people with mild T2D; standards of care dictate that they should receive medical therapy and metformin is the drug most often recommended in this context (23). Metformin is also the only drug that has been recommended for use in diabetes prevention (24). Thus, we will be comparing gastric banding to the current standard of medical monotherapy early in the course of T2D.

We will study people with pre- and mild T2D because we have observed a fairly linear decline in  $\beta$ -cell compensation across this range (9). We are also confident that we can assess insulin sensitivity and secretion across this range. Thus, we will be able to test for arrest or reversal of falling  $\beta$ -cell compensation. Overall, this approach and our expertise  $\beta$ -cell biology and preservation in humans put us in very strong position to make unique and important contributions to the RISE Consortium.

## 2.4 Rationale for Outcome Measures

We plan to employ technically complex "gold standard" measures for a high degree of scientific rigor in this relatively small study, together with simpler surrogate measures that could be applied in larger studies and in clinical settings. The complex measures will be made with intravenous stimuli (glucose, arginine). The simpler measures will be made in the fasting state (HOMA, biomarkers) and in response to oral glucose.

#### 2.4.1 Intravenous-Based Tests of ß- and $\alpha$ -cell Function and Insulin Sensitivity

Glucose tolerance is dependent on  $\beta$ -cell function and insulin sensitivity, and both of these can be quantified using the hyperglycemic clamp (25). Although  $\alpha$ -cell function dysregulation occurs in type 2 diabetes, the exact role of  $\alpha$ -cell function in determining glucose tolerance is not well defined.

The acute insulin response to intravenous glucose (AIRg), also known as the first-phase insulin response, occurs within the first ten minutes following glucose administration and is a sensitive marker of ß-cell function that decreases as the fasting glucose level rises. A potential limitation of this measure is that it becomes zero or negative when fasting glucose approaches the diabetic range (26). Since we will include people in this range, the AIRg is not the ideal primary outcome.

The second-phase insulin response to intravenous glucose begins at the time of glucose administration and continues for as long as the glucose level remains elevated. It is frequently quantified as part of a hyperglycemic clamp. Unlike AIRg, this particular response generally persists even when the fasting glucose concentration is in the diabetic range.

The prevailing glucose level modulates the  $\beta$ -cell secretory response to non-glucose secretagogues such as peptides and amino acids. By performing hyperglycemic clamps with the addition of arginine, it is possible to quantify the maximum insulin response (AIRmax), which has been shown to correlate with  $\beta$ -cell mass in animal studies (27).

Normally,  $\beta$ -cell responses are modulated by the prevailing insulin sensitivity. Thus, adjusting the proposed  $\beta$ -cell measures for the degree of insulin sensitivity (S1) provides a measure of compensation for insulin resistance, a measure of  $\beta$ -cell function that declines consistently

during progression to and of T2D (3;28). The most widely used approach is calculation of a disposition index, a product of measures of insulin sensitivity and secretion based on demonstration of a hyperbolic relation between the two variables. AIRg (29;30), second phase insulin (31), and AIRmax (32;33) have been shown to have such relationships. Insulin sensitivity can be calculated from the hyperglycemic clamp as the ratio of steady state glucose infusion rates to steady state plasma insulin levels. We plan to examine relationships between  $\beta$ -cell measures and insulin sensitivity from the hyperglycemic clamp and use the disposition index or another, more appropriate method to adjust beta cell function for insulin sensitivity in primary and secondary analyses.

The reciprocal of glucose's ability to potentiate the  $\beta$ -cell response is its ability to suppress the  $\alpha$ -cell response. This function can also be measured using hyperglycemic clamps along with arginine. The minimum acute glucagon response at maximal glycemic suppression (AGRmin) is greater in people with type 2 diabetes, indicative of impaired  $\alpha$ -cell regulation (30).

#### 2.4.2 Oral-Based Tests of ß- and $\alpha$ -cell Function and Insulin Sensitivity

The oral glucose tolerance test (OGTT) also provides measures of islet function and has been used in large clinical trials. The early insulin response (insulinogenic index) is an important determinant of glucose tolerance (14). This response, when used in combination with a fasting measure of insulin sensitivity (1/fasting insulin, HOMA), provides another estimate of ß-cell function termed the oral disposition index (DIo) (20). Using modeling approaches such as those developed by Mari et al (63) and Cobelli et al (ref), it is possible to obtain a number of additional parameters of ß-cell function and insulin sensitivity. In addition, insulin secretion rates can be calculated from the OGTT (64). Finally, overall glucose tolerance can be calculated from the test (57).

Physiological glucagon suppression during an OGTT is an important determinant of glucose tolerance and provides an estimate of  $\alpha$ -cell function. In individuals with type 2 diabetes, this response is increased compared to normal subjects (2; 26; 27).

These OGTT-based measures will be made in the study and will be used to determine their relationship to assessments made using intravenous tests both at baseline and with intervention. OGTT-derived measures can be evaluated for cross-sectional relationships with clamp-derived measures and for value as prospective predictors of therapeutic response.

#### 2.4.3 Biomarkers

The detailed measures of  $\beta$ -cell function that we will be making provide an opportunity to identify biomarkers that can predict deterioration of  $\beta$ -cell function and/or response to

interventions that can mitigate such deterioration. The identification of such biomarkers is an important ancillary goal of the RISE Consortium. Because of budget constraints, the focus during this stage of the project will be on collecting patient specimens that can used in the future for identification of biomarkers once the main outcomes of the study are known. We will collect samples that can be used to examine previously described peptide markers of diabetes risk (e.g., adiponectin, ferritin, ApoB, C-reactive protein, IL-2 receptor A (34-37) and evolving markers of  $\beta$ -cell mass regulation (e.g., prolactin, DNA fragments and methylation, GLP-1, GIP, HSP90nucleic acids (38-42). We will also collect serum samples that can be analyzed using genomic, micro-RNA, proteomic and metabolomics approaches comparing for example responders to non-responders to the study interventions.

# **3 STUDY DESIGN**

## 3.1 Overview and Rationale

The BetaFat study protocol described herein will involve 88 adults who are 20 – 65 years old and who have prediabetes or drug-naïve, recent onset and mild type 2 diabetes. Additional inclusion and exclusion criteria are defined below. Participants will be randomized over a 27 month period to either metformin or gastric banding in an open treatment format. The primary outcome will be rate of change in ß-cell compensation for insulin resistance, as defined below. Figure 3 provides an overview of the types and timing of main study procedures.

# 3.2 Primary Endpoints

The primary objective of the RISE Study is to evaluate the effects of randomized treatment on ß-cell function, measured by hyperglycemic clamp techniques. Given that insulin and C-peptide are both used in quantifying ß-cell function, each of them will be measured in certain or all tests in part to avoid the problem of collinearity when performing the statistical analyses. Two co-primary endpoints are specified:

- Change between baseline and end study in ß-cell function measured as the second phase response (steady-state of the hyperglycemic clamp; 100-120 minutes of glucose infusion). This will be calculated as mean C-peptide at steady state, adjusted for insulin sensitivity (ratio of the glucose infusion rate:plasma insulin concentration at steady state).
- Change between baseline and end study in β-cell function measured as AIRmax (arginine-induced acute insulin response at hyperglycemia glucose; β-cell secretory capacity) [30]. This will be calculated as the incremental area under the C-peptide curve from 0-10 minutes following arginine injection at a plasma glucose ≥450 mg/dl, adjusted for insulin sensitivity measured by the hyperglycemic clamp.

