#### 3.3.1 Hyperglycemic clamp-derived ß-cell measures

- a. First phase insulin response (incremental insulin area from 0-10 minutes after initial glucose bolus)
- b. First phase C-peptide response (incremental C-peptide area from 0-10 minutes after initial glucose bolus)
- c. Disposition index derived from a and b, using hyperglycemic clamp-derived measure of insulin sensitivity (glucose disposal rate/insulin: GDR/I)
- d. Second phase insulin response, with adjustment for insulin sensitivity
- e. AIRmax response to arginine calculated using insulin concentrations and adjusted for insulin sensitivity

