## 3.3.4 $\alpha$ -cell Function

- a. Glucagon suppression in response to sustained hyperglycemia during the clamp (the decrement in glucagon concentration from baseline to nadir value at 100-120 minutes)
- b. Acute glucagon response arginine (the incremental increase in glucagon concentration from pre-arginine baseline for the 10 minutes after the arginine injection)
- c. OGTT-derived measures: integrated glucagon response from 0-120 minutes
- d. Fasting sample-derived measures: glucagon

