## 4.6 Masking

No masking will be employed. The study team and each individual participant will be aware of his/her treatment allocation.

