## 6.2.3 Hyperglycemic Clamp

Hyperglycemic clamps (at approximately 200 mg/dl) will be performed after a 10-12 hour overnight fast at baseline and at 12 and 24 months after initiation of metformin or placement of gastric bands. The clamp procedure will incorporate 3 main sets of blood sampling for the planned outcome measurements: first phase (0-10 minutes); second phase (100-120 minutes); and maximal stimulated responses (from 10 minutes before until 10 minutes after arginine injection once plasma glucose has been raised to~450 mg/dl). A priming glucose bolus will be used to stimulate first phase responses, a continuous dextrose infusion will be used to create steady state hyperglycemia at ~200 mg/dl for second phase and then raise glucose to ~450 mg/dl for maximum response to arginine. Arterialized venous blood samples will be obtained at 5-min intervals throughout for measurement of plasma glucose concentration to guide the glucose infusion.

For the OGTT and clamp measures, participants will be asked to refrain from vigorous exercise and tobacco use for 24 hours before the initiation of testing. Study medications will be withheld the morning of testing.

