# **9 STATISTICAL CONSIDERATIONS**

All analyses will be conducted under the intention-to-treat principle using the treatment as assigned to each subject, and using all available data from all subjects. We will assess the distributional characteristics of all variables and will adjust the analysis accordingly by employing transformations or robust (model free) or nonparametric (distribution free) methods.

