# 9.5 Handling of Missing Data

It is anticipated that a small number of participants may reach HbA1C >8.0% on two visits and, thus, have primary outcomes completed prior to 24-months. If follow-up time between baseline and end-of-trial differ between the two intervention groups, we will use rate of change (defined as (baseline-end-of-trial)/follow-up time) as the outcome in the analysis to take into account of differential follow-up time.

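### Do the two wordings of the glucose level for arginine injection (≥450 and ~450 mg/dl) leave the co-primary AIRmax endpoint undefined?

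*Combined protocol and SAP*

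**What the plan says.** Section 3.2 names two co-primary endpoints. The second, AIRmax, is the incremental C-peptide area over the 10 minutes "following arginine injection at a plasma glucose ≥450 mg/dl", adjusted for insulin sensitivity from the clamp.

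Section 6.2.3 describes how the clamp is run. It mentions the arginine step twice: "arginine injection once plasma glucose has been raised to~450 mg/dl" and "raise glucose to ~450 mg/dl for maximum response to arginine". The lower plateau, near 200 mg/dl, is also given only approximately. Plasma glucose is measured every 5 minutes throughout to steer the infusion.

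Two secondary endpoints come from the same injection, and neither restates a glucose level. Section 3.3.1(e) is the "AIRmax response to arginine calculated using insulin concentrations and adjusted for insulin sensitivity". Section 3.3.4(b) is "the incremental increase in glucagon concentration from pre-arginine baseline for the 10 minutes after the arginine injection".

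Section 9 sets an intention-to-treat analysis "using all available data from all subjects". Section 9.1 specifies ANCOVA adjusted for baseline, with each co-primary endpoint tested at 0.05. Section 9.5, on missing data, deals only with early completion, expecting that "a small number of participants may reach HbA1C >8.0% on two visits", and with unequal follow-up time. Section 4.6 says there is no masking: "The study team and each individual participant will be aware of his/her treatment allocation".

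**The concern.** A floor and an approximate target are different statements. Neither Section 3.2 nor Section 6.2.3 says what happens to an injection given slightly below 450 mg/dl. The literal definition in Section 3.2 would leave it out, the general principle in Section 9 would keep it, and Section 9.5 does not mention it.

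Three features of the trial make this look important:

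- AIRmax is tested at the full 0.05 without adjustment for the other co-primary endpoint, so it could support a positive claim alone.
- The staff know the allocation. A case-by-case decision on borderline clamps could therefore be coloured by the arm.
- Section 2.4.1 says the prevailing glucose level affects how strongly β-cells respond to stimuli such as arginine, so the glucose reached bears on the value measured.

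If such clamps were dropped, the number analysed for AIRmax would fall. The loss might also differ between arms, because both treatments aim to change insulin resistance and that could affect how easily the target is reached.

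**Working it through.** **1. Do the wordings conflict?** The possible cases are:

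| Glucose at injection | Section 6.2.3 (~450) | Section 3.2 (≥450) |
|---|---|---|
| At or a little above 450 | met | met |
| Slightly below 450 (e.g. 440, or 10/450 = 2.2% under) | met | not met literally |
| Far below 450 | not met | not met |

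Only the middle row is in doubt. Staff who raise glucose to at least 450 and then inject satisfy both sections, and the 5-minute samples let them see when that point is reached. The documents give no distribution of achieved glucose, so the share of clamps in the middle row is unknown.

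**2. Does the plan supply a default for that row?** Section 9 uses all available data from everyone randomised. No section excludes a clamp that was performed or makes its inclusion depend on achieved glucose. The default is to keep it.

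**3. Would the C-peptide and insulin versions use different clamps?** Section 3.3.1(e) reuses the name AIRmax and changes only the analyte. The natural reading is that the stimulus defined in Section 3.2 carries over. For glucagon, Section 2.4.1 describes the arginine measure at maximal glycemic suppression, which is the same upper plateau. Nothing suggests separate sets of clamps.

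**4. The plan's power figures.** Inputs from Section 9.3 are 44 randomised per group, 10% loss per year, two-sided α = 0.05 and baseline–follow-up correlation r = 0.5.

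- Completers: 44 × 0.8 = 35.2, or 44 × 0.9² = 35.6. The plan says about 35.
- Two-sample t-test with n = 35 per group (non-central t): effect detectable at 80% power 0.679. The plan says 0.68.
- ANCOVA divides the effect by √(1 − r²) = √0.75 = 0.866. Detectable effect: 0.679 × 0.866 = 0.588. The plan says 0.59.
- ANCOVA power at 0.68: 0.68/0.866 = 0.785, which gives 89.9%. The plan says 89%.

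The figures reproduce. With every clamp kept, n stays at 35, and power is 80% at 0.59 and 97% at the plan's projected difference of about 0.80.

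**5. What if the clamps were dropped, contrary to Section 9?** The reduced n below are assumptions, since the documents give no basis for them. Same ANCOVA formula, df = 2n − 3:

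| n per group | Power at 0.59 | Power at 0.80 |
|---|---|---|
| 35 | 80% | 97% |
| 32 | 76% | 95% |
| 28 | 71% | 92% |
| 22 | 60% | 85% |
| 20 | 56% | 81% |
| 19 | 53% | 79% |

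At the projected 0.80, power stays above 80% until more than 35 − 20 = 15 per group are lost. At the smallest effect the plan claims to detect, 0.59, any loss takes power below 80%. This describes an exclusion that no section proposes, so it says nothing against the plan as written.

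**The case for a change.** The strongest case for a change is that the general principle in Section 9 does not settle the question. A commitment to use all available data presupposes that the value is a valid measurement of the endpoint. On the literal text of Section 3.2, a response obtained at 440 mg/dl is arguably not AIRmax at all. In an unmasked trial, the definition of a co-primary endpoint should leave no such discretion, and one sentence would remove it at almost no cost. Glucose is already sampled every 5 minutes, so reporting the level reached would need no new measurement. Section 7.4.7 also commits to limiting concentrated glucose solutions, which might make the target harder to reach.

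Part of this stands. The documents do not state a rule in so many words, and a stated rule would be tidier. The manual of procedures, on which staff training is based (Section 11.3), may hold a tolerance. It was not available, so the rule can be called absent only from these documents.

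The step from there to a flaw does not stand. Harm requires that sub-450 injections occur in some number, that someone sets aside the principle in Section 9 to exclude them, and that the exclusions differ by arm. The documents support none of these steps. Section 4.6 shows only that allocation is known, and achieved glucose is a recorded measurement rather than a judgement. The obvious remedy, keeping the clamp in the main analysis, is what Section 9 already implies. A strict cut-off or a tolerance band would be a trade-off: it would make the stimulus more uniform at the price of losing randomised participants after treatment has begun.

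**Conclusion.** The difference in wording is real, but no change to the plan is needed. Section 3.2 states an endpoint condition and Section 6.2.3 an approximate operating target. They agree for every clamp that reaches at least 450 mg/dl. For a clamp slightly below that level, the intention-to-treat commitment in Section 9 supplies a sensible default, and no section overrides it.

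The size of any effect cannot be determined, because the documents do not say how often glucose would fall short. Under the default, no participant is lost for this reason, and the figures in Section 9.3 (35 per group, 0.68, 89%, 0.59) stand without error.

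The conclusion assumes that analysts follow Section 9 for all performed clamps in both arms, and that the manual of procedures contains no contrary rule. Which glucose level is right is not judged here. The two sections could be worded alike when the protocol is next revised, and the glucose reached at injection could be reported by arm, but the soundness of the AIRmax comparison depends on neither.
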